9.3.1. Replacement of Subjects

9.3.1.1. Single-dose Phase

In the single-dose phase, up to 3 dose cohorts of 5 subjects may be studied (doses to be determined by IDMC) for each age group (see Table 7). Enrollment in each cohort will continue until at least 5 evaluable subjects are completed. To be considered an evaluable subject, each subject must meet the following criteria:

1. Receive expected dose of study drug
2. Complete at least 4 hours of post-dose assessments
3. Complete at least 3 PK assessments

9.3.1.2. Multiple-dose Phase

In the multiple-dose phase, a single dose cohort (dose to be determined by IDMC) will be studied for each age group (see Table 8). Subjects will not be replaced in the double-blind multiple-dose phase.

10. TREATMENT OF SUBJECTS

10.1. Study Visits

The Schedule of Events to be performed at each visit is shown in section 3. Provided below are further details where additional instruction about the assessments that will be performed is deemed to be needed.

10.1.1. Subject Screening

Investigators will be expected to maintain a screening log of all potential study subjects. This log will include limited information about the potential subject and the date and outcome of the screening process (eg, enrolled into the study, reason for ineligibility, or refused to participate). Investigators will provide information about the study to subjects who appear to meet the criteria for participation in the study.

10.1.2. Pretreatment/Screening Assessments

After obtaining informed consent, the full assessment of eligibility will be conducted and prior to randomization/study entry (depending on study phase), pretreatment/screening assessments will be performed according to the Schedule of Events outlined in section 3.

10.1.3. Study Entry

A subject whose parent or guardian gives written informed consent and who satisfies all eligibility criteria may be entered into the study. The following demographic information will be required for study entry:

- Subject initials
- Date of birth
- Gender
- Weight

Demographic (and other study specific details) will be entered into the IWRS. At the end of the randomization procedure, the subject will be assigned a unique subject identification number in sequential order.

The subject identification number will consist of 8 digits. The first 4 digits represent the study site number followed by -1001, -1002, -1003, and so on.

10.1.4. Study Assessments

All study assessments will be conducted in accordance with section 8 and the Schedule of Events outlined in section 3.

10.1.5. Follow-up

A documented follow-up telephone call will be required 3 days and 14 days after the last dose of study drug. Site staff will collect information regarding new AEs (including SAEs) or resolution of ongoing AEs/SAEs, including concomitant medications being used to treat any SAE or ongoing AE and any new analgesic medications started after EOT or ET.

The date of EOT or ET from the study will be recorded by the Investigator (or assigned designee) and will be the official EOT/ET for each subject. Subjects may take analgesics (opioid or non-opioids) according to SOC after EOT. Study participation will end with the completion of the 14-day follow-up telephone call.

10.2. Prior and Concomitant Medications and Procedures

Drugs that are allowed and not allowed as concomitant medications for either episodic or chronic use are described in this section. Following execution of the informed consent, any concomitant medication (including vitamin supplements, herbal remedies, and nonprescription medications) used while the subject is on study drug (up to 24 hours post first dose of study drug) will be recorded. Surgical medications will be captured on the Surgical Medications eCRF. Medications as noted in [Appendix B](#) will be entered into the eCRF. The medication name, dose, date, time, and indication for use will be recorded. The Medical Monitor should be notified in advance of (or as soon as possible after) any instances in which prohibited therapies are administered. Medications and therapies that are considered necessary for the subject's welfare and will not interfere with the response to the study drug may be given at the discretion of the Investigator. Medications known to have analgesic effects or to influence the subject's perception of pain must be avoided during the study except as provided for in the protocol. The following restrictions will apply starting with the post-operative period:

- For all age groups: During the single-dose phase, no analgesics other than the study drug (except NCA) will be permitted for 6 hours after study drug administration. Non-opioid analgesics (acetaminophen and/or NSAIDs) per SOC may be used to treat breakthrough pain not earlier than 6 hours after administration of study drug.
- Nursing mothers should be advised not to receive opioids during the study period.
- During the multiple-dose phase (all age groups), no analgesics other than the study drug will be permitted during the 24-hour assessment period (except NCA rescue).
- Across all age groups, acetaminophen or SOC may be administered for subjects who develop fever during the study period.
- Central nervous system (CNS) depressants, muscle relaxants, and antihistamines, which have been given regularly (unchanged dose [$\pm 10\%$] and dosing frequency) during the pre- and/or postoperative period, and will be given at the same dose and dosing frequency during the study period, will be permitted; otherwise these medications will be prohibited from 4 hours prior to stopping postoperative IV opioid pain medication until the completion of study observations.
- SOC may be given for pruritus or as a sleep aid.

- Antidepressant therapy (excluding MAOIs) will remain stable (unchanged dose [$\pm 10\%$] and dosing regimen) throughout the study.

Constipation is the most common opioid AE. Laxatives should be used at the Investigator's, or designee's, discretion during treatment with study drug and recorded as a concomitant medication.

Nausea and vomiting are common opioid-induced AEs. It is expected that some of the subjects will need to be administered an antiemetic. Any antiemetic used during treatment with study drug should be recorded as a concomitant medication.

10.2.1. Prohibited Medications

During the study, the following medications are prohibited:

- Preoperative opioids administered for a period of more than 72 hours in duration.
- Any investigational drugs other than oxymorphone HCl immediate-release oral liquid from 30 days prior to screening through EOT.
- Oxycodone or oxymorphone within 48 hours prior to screening.
- Cough syrup containing an opioid from screening through EOT.
- MAOIs from screening through EOT
- Products containing caffeine or xanthine.
- Non-opioid analgesics (acetaminophen and/or NSAIDs) during the Multiple-dose Phase

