9.3. Subject Discontinuation Criteria

A premature discontinuation will occur when a subject ceases participation in the study, regardless of circumstances, prior to the completion of the protocol. Subjects can be prematurely discontinued from the study for one of the following reasons:

- An AE
- Lack of efficacy
- Use of an opioid antagonist (eg, naloxone)
- A protocol violation (reason must be specified, for example: lack of compliance, use of a prohibited concomitant medication, failure to meet inclusion/exclusion criteria after study entry, etc.)
- Withdrawal by subject (reason must be specified)
- The subject was “lost to follow-up”
- Unblinding of a subject based on medical need
- Sponsor decision to terminate trial
- Investigator decision

Other Reasons (reason must be specified)

If a subject discontinues from the study, all EOT procedures should be conducted as detailed in section 3. The date a subject discontinues the treatment and the reason for discontinuation will be recorded in the source documentation and electronic Case Report Form (eCRF). If, however, a subject withdraws consent, no EOT procedures are required except for the collection of AE information. This information should be recorded in the source documentation and the eCRF.

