14.2.1.2. Multiple-dose Phase

The safety population for the multiple-dose phase will include all subjects who receive at least 1 dose of study drug or placebo. All safety analyses for the multiple-dose phase will be performed using this population and in all safety analyses, subjects will be attributed to the treatment that they actually received regardless of their assigned randomized treatment.

The intent-to-treat (ITT) population will include all randomized subjects who receive at least 1 dose of study drug during the multiple-dose phase and complete at least 1 post-dose pain intensity assessment. All efficacy analyses and demographic/baseline characterization will be performed using this population and in all efficacy analyses subjects will be attributed to the randomized treatment regardless of the treatment they actually receive.

The per-protocol (PP) population will include all subjects in ITT population who do not violate the protocol in any fundamental manner related to the evaluation of efficacy. This population will be used for supporting the primary efficacy analysis.

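### Acetaminophen for fever is both permitted and prohibited in the multiple-dose phase, and no rule says how such use counts for deviations or the per-protocol set

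*Protocol*

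**What the plan says.** **Permission.** Protocol Section 10.2 states: "Across all age groups, acetaminophen or SOC may be administered for subjects who develop fever during the study period". Section 8.1.3 has the same sentence as a separate bullet, directly after a breakthrough-pain rule that is expressly confined to the single-dose cohorts. The fever sentence has no such limit.

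**Prohibition.** Section 10.2.1 lists among the prohibited medications "Non-opioid analgesics (acetaminophen and/or NSAIDs) during the Multiple-dose Phase". It makes no exception by indication. SAP Section 3.6.1 carries the same item, and the SAP does not mention the fever permission. Section 10.2 adds that in the multiple-dose phase "no analgesics other than the study drug will be permitted during the 24-hour assessment period (except NCA rescue"; nurse-controlled morphine is the only exception given there.

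**General clause.** Section 10.2 also says that drugs with analgesic effect "must be avoided during the study except as provided for in the protocol".

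**Consequences.** Section 9.3 gives "use of a prohibited concomitant medication" as an example of a protocol violation, under a lead-in that reads "Subjects can be prematurely discontinued from the study for one of the following reasons". Section 9.3.1.2 rules out replacement in this phase. Section 14.2.1.2 defines the per-protocol set as ITT subjects "who do not violate the protocol in any fundamental manner related to the evaluation of efficacy" and does not mention antipyretics. SAP Section 4.3 has the sponsor's study team grade each deviation as major or minor before database lock.

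**The concern.** Two current rules give the same event opposite status. One site can treat a febrile infant with acetaminophen and regard this as allowed. Another can record it as prohibited medication, notify the Medical Monitor and consider withdrawal. The difference would come from which section was read, not from anything about the infant.

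The drug is relevant to the endpoint. Section 11.1.1 makes cumulative morphine, background plus boluses, the primary efficacy variable. The protocol itself classes acetaminophen as a non-opioid analgesic and lets it be used for breakthrough pain in the single-dose phase from 6 hours after dosing. A dose given for fever is still a dose of a co-analgesic and could lower morphine demand in whichever arm received it.

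Three things are at stake: uniform conduct, membership of the per-protocol set, and the major or minor grade of the deviation. SAP Section 4.3 takes deviations from monitoring reports and does not derive them by program. Whether fever use appears as a deviation at all may therefore depend on how each monitor read the protocol.

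**Working it through.** **1. The rules side by side, for acetaminophen given for fever in the multiple-dose phase**

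| Source | Status | Window | Exception stated |
|---|---|---|---|
| Protocol 8.1.3, fever bullet | Allowed | Study period | Not needed |
| Protocol 10.2, fever bullet | Allowed | Study period | Not needed |
| Protocol 10.2, multiple-dose bullet | Not allowed | 24-hour assessment period | NCA rescue only |
| Protocol 10.2.1 | Prohibited, drug named | Multiple-dose phase | None |
| SAP 3.6.1 | Prohibited, drug named | Multiple-dose phase | None |

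No section says which rule takes precedence. The conflict is in the current text and does not depend on the summary of changes.

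**2. The windows also differ.** The last dose may come up to 18 hours after the first (Section 8.1.6), and end of treatment is 24 hours after the last dose (Section 8.1.7). The span from first dose to end of treatment can reach 18 + 24 = 42 hours. The bar in Section 10.2 covers a 24-hour period, so between hour 24 and hour 42 it may have lapsed while the ban in Section 10.2.1 may still run.

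**3. Which analysis sets are touched.**
- ITT (Section 14.2.1.2) needs randomization, at least one dose and at least one post-dose pain assessment, and analyses subjects as randomized. Later acetaminophen, or later withdrawal, does not normally undo any of these.
- Section 14.5 names ITT as the primary population. The per-protocol analysis is supportive (Section 14.5.3).
- Per-protocol membership turns on whether the violation is fundamental to the evaluation of efficacy. The documents do not say whether fever use is.

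**4. The plan's sample size, for scale only.** Inputs from Section 14.1.1 are effect size 0.9, two-sided 0.05 and 80% power. The normal approximation gives n = 2 × (1.960 + 0.842)² / 0.9² = 19.4, rounded up to 20 per arm, so the stated figure reproduces. Power at 20 per arm is 81.2% (normal) or 79.2% (two-sample t).

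Two-sample t power if infants were left out of an analysis set altogether:

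| Analysed per arm | Infants left out of 40 | Power |
|---|---|---|
| 20 and 20 | 0 | 79.2% |
| 20 and 19 | 1 | 78.1% |
| 20 and 18 | 2 | 76.9% |
| 18 and 18 | 4 | 74.6% |
| 16 and 16 | 8 | 69.3% |

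The numbers left out are assumptions, because no fever or acetaminophen rate is given. By step 3, the table could describe a per-protocol analysis but not the primary ITT analysis.

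**The case against.** **The rules can be harmonised.** The general clause in Section 10.2 lets analgesics be used where the protocol provides for it. The fever bullet follows directly after the multiple-dose ban and is tied to an indication, so it can be read as such a provision. This is a fair reading, and the fault may be no more than a missing cross-reference. It does not settle the matter: the multiple-dose bullet names one exception only, and Section 10.2.1 then bans acetaminophen by name with no exception.

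**Withdrawal does not follow.** This stands. Section 9.3 is permissive, and Section 10.2 handles prohibited therapy by notice to the Medical Monitor, in advance or as soon as possible afterwards. A reader might infer that a febrile infant must be discontinued; nothing in the documents says so.

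**The trial does not lose power.** This also stands for the primary analysis. A reader might infer that, without replacement, each febrile infant costs 5% of an arm (1/20). ITT would normally keep the infant. Even in a per-protocol analysis, one exclusion costs about 1 point of power (79.2% to 78.1%), and falls to 75% or 69% need 4 or 8 exclusions. The documents support no such count.

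**Recording is already covered.** Section 10.2 requires name, dose, date, time and indication, and Section 8.1.3 requires precise dose, frequency and indication. No new data item is needed.

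**Cutting cumulative morphine at the first antipyretic would not help.** Agreed. It would give infants unequal observation windows, ended by a post-randomization event that treatment may influence.

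**Efficacy analyses have been dropped.** SAP Sections 7.6 and 8 confirm this after early termination. That limits the practical effect but does not remove it: SAP Section 7.2 still summarises major and minor deviations for the multiple-dose phase.

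**Conclusion.** The contradiction holds. In the multiple-dose phase, acetaminophen for fever is compliant under Protocol Sections 8.1.3 and 10.2 (fever bullet) and is use of a prohibited medication under Section 10.2.1 and SAP Section 3.6.1. The infant may be discontinued but need not be.

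The consequence is limited to conduct across sites, per-protocol membership and deviation grading. The primary ITT set would normally keep the infant, so the point is no criticism of the sample size or of power for the primary analysis. A co-analgesic could still influence morphine demand within ITT, but the documents give no basis for the direction or size of any difference between arms.

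The number of infants affected is unknown. The conclusion rests only on the wording of the sections compared, not on any assumed fever rate. It should be corrected because two stated rules conflict and the correction is cheap. It does not threaten the safety report that the SAP now plans, beyond the deviation tables and listing.

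**What to change.** 1. Reconcile Protocol Sections 8.1.3, 10.2 and 10.2.1 and SAP Section 3.6.1 so that acetaminophen or other standard-of-care treatment for fever in the multiple-dose phase has one stated status and one time window. Which rule to adopt is for the sponsor and its clinical advisers; this review does not choose.
2. State, before unblinding and in time for the deviation review under SAP Section 4.3, whether such use is a major deviation, a minor one or none, and whether it excludes the infant from the per-protocol set. Apply that rule to every site's records, however the site itself classed the event.
3. If efficacy is ever analysed, report antipyretic-analgesic use by arm and keep these infants in the ITT analysis.

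The cost is a few lines of wording, one deviation rule and, only if efficacy is analysed, one descriptive table from data already required. Changing the text now cannot alter conduct that has already taken place, so for subjects already treated the second step matters most.

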10.3. Treatment Compliance

Discrepancies between the number of doses administered and the amount of returned drug will be recorded in the drug accountability log. The Investigator (or an authorized designee) will perform a review for compliance by reviewing the source documentation and eCRF against used and returned study drug and discussing any variations from the protocol-defined dosing schedule with study personnel. Compliance and accountability will be recorded on the Drug Accountability Forms that will be provided to each clinical site. Any suspicion of diversion will be carefully investigated by the Sponsor. Accidental or intentional overdoses should be reported to the Sponsor/designee promptly (section 12.6.1.1).

10.4. Blinding and Randomization

Subjects will be stratified by 4 different age groups as outlined in Table 7 and Table 8. During the multiple-dose phase, subjects within each age group will be randomized to receive either oxymorphone HCl or placebo in a 1:1 ratio.

Site personnel will be trained on the randomization component of the study.

10.4.1. Blinding

The multiple-dose phase of this study is double-blinded. Subjects, parents, study staff (with the exception of the Pharmacist), clinical staff, vendor staff (eg, CRO) with the exception of the

packaging and labeling vendor, and the Sponsor (with the exception of the clinical supplies staff) and its designees will be blinded to the study treatment being received by each subject. In addition, an unblinded monitor will conduct study medication reconciliation at the site. The blind will only be broken in cases of medical need, and every attempt will be made to discuss the case with the Medical Monitor prior to unblinding. Instructions for unblinding subjects during the course of the study will be provided. Breaking the code at the investigative site will immediately disqualify the subject from further participation in the study. In addition, the event(s) leading to emergency unblinding must be reported as an SAE according to instructions in section 12.5.2. Otherwise, the study will be unblinded only after database lock and after all Sponsor-required authorizations have been documented.

11. ASSESSMENT OF EFFICACY

11.1. Primary Efficacy Measurements

11.1.1. Morphine Consumption via NCA

NCA is an established form of postoperative analgesia, similar in nature to other demand-led analgesic regimens (eg, PCA), but tailored for patients who are too young or unable to use PCA.(14-18). The primary efficacy variable will be the cumulative total amount of morphine required for analgesia (including background infusion and boluses).

11.2. Secondary Efficacy Measurements

The Investigator, or designee will conduct pain assessments at the designated times during the study (Table 3 and

Table 4) using the FLACC or NIPS (Appendix C and Appendix D, respectively).

Selection of pain scales in children is complex because there is no single instrument suitable for all ages. While the use of a VAS is commonly employed in adults for the assessment of pain, the use of a VAS in young children is complicated by communication barriers. The selection of data collection instruments in this study is based on those with the widest acceptability and best evidence of psychometric properties regarding the appropriateness in the target population. The Pediatric Initiative on Methods, Measurement and Pain Assessment in Clinical Trials (Ped-IMPACT) recommended core outcome domains (including pain intensity) to be considered in clinical trials for acute and recurrent/chronic pain, which included the FLACC.(20)

11.2.1. Face, Legs, Activity, Cry, Consolability (FLACC)

The Ped-IMPACT consensus concluded that self-reported measures of pain intensity, alone, are not sufficiently valid for children <3 years of age.(20) There is wide variability in young children's ability to use self-report measures especially between the ages of 3 and 7 years of age, so it would be reasonable to use a behavioral observational measure as an outcome measure in this age group.(21) The FLACC scale (Appendix C) is a well-established observational behavioral measure that is based on a 5-item scale that raters use to score each of 5 categories of pain response, namely, (F) Face; (L) Legs; (A) Activity; (C) Cry; and (C) Consolability, which are scored from 0 to 2 (Appendix C).(22) There are extensive reliability and validity data on the FLACC, including preverbal children.(22,23) The FLACC uses items similar to other well-established instruments, but with a more easily understood 0 to 10 scale.(24) It has a low users' burden and excellent inter-rater reliability. The FLACC has demonstrated moderate concurrent validity with FACES and good concurrent validity with VAS. The Ped-IMPACT consensus recommended the FLACC as an observational measure of acute pain intensity in children 1 year and above.(20) Moreover, a Task Force approved by the American Society for Pain Management and Nursing Board of Directors recommended the use of the FLACC in subjects aged 2 months to 7 years for post anesthesia care, in the intensive care unit, in acute care settings, for surgical pain, and for acute pain.(22-26) In the current study, the FLACC will be used in all subjects aged 61 days to <2 years for pain assessment (Groups A and B). Each rater will receive training on completing this observer-reported pain assessment; completion of the training will be documented.

